11.4.2.1 Reported within 24 Hours

Serious Adverse Events requiring reporting within 24 hours (as described above) must also be reported to the UWCCC DSMC within one business day. See 11.4.2.1.1. SAEs will also be reported to Collectar Biosciences within 24 hours of discovery of the event. The OnCore SAE Details Report must be submitted along with other report materials as appropriate (FDA Medwatch Form #3500 and/or any other documentation available at that time of initial reporting). Within 10 working days, all available subsequent SAE documentation must be submitted electronically along with a 24 hour follow-up SAE Details Report and a completed UWCCC SAE Routing Form to [contact]. All follow up SAE documentation will also be submitted to Collectar Biosciences ([contact]). All information is entered and tracked in the UWCCC database.

The Principal Investigator notifies all investigators involved with the study at the UWCCC, the IRB, and Collectar Biosciences.

11.4.2.1.1 Report to the UWCCC, and Collectar Biosciences:

Reference the **SAE SOP** (Standard Operating Procedure) and the **SAE Reporting Workflow for DOTs** on the UWCCC website (<http://kb.wisc.edu/uwccc>) for specific instructions on how and what to report to the UWCCC for [24] hour initial and follow-up reports. **A follow-up report is required to be submitted within 10 days of the initial [24] hour report.**

For this protocol, the following entities are required to be notified:

- a. [contact]
- b. UWCCC PIs: [name] [name] and [name]
- c. UWCCC PM: [name]
- d. Collectar Biosciences ([contact])
- e. Medpace: [contact]
- f. Any other appropriate parties listed on the SAE Routing Form (for follow-up reports only)

11.4.2.1.2 Report to the IRB

Consult the UW-IRB website for reporting guidelines.

11.4.2.2 Reported within 10 Calendar Days

Serious Adverse Events requiring reporting within 10 calendar days (as described above) must also be reported to the Data and Safety Monitoring Board (DSMC) Chair via an email to [contact]. SAEs will also be reported to Collectar Biosciences. The OnCore SAE Details Report must be submitted along with other report materials as appropriate (FDA Medwatch Form #3500 and/or any other documentation available at the time of initial reporting). The UWCCC DSMC Chair will review the information and determine if further action is required. All information is entered and tracked in the UWCCC database.

The Principal Investigator notifies all investigators involved with the study at the UWCCC, the IRB, and Collectar Biosciences.

11.4.2.2.1 Report to the UWCCC and Collectar Biosciences:

Reference the **SAE SOP** and the **SAE Reporting Workflow for DOTs** on the UWCCC website (<http://kb.wisc.edu/uwccc>) for specific instructions on how and what to report to the UWCCC for [10] day reports.

For this protocol, the following entities are required to be notified:

- a. [contact]
- b. UWCCC PIs: [name] [name] and [name]
- c. UWCCC PM: [name]
- d. Collectar Biosciences ([contact])
- e. Medpace: [contact]
- f. Any other appropriate parties listed on the SAE Routing Form (for follow-up reports only)

11.4.2.2.2 Report to the IRB:

Consult the UW-IRB website for reporting guidelines.

11.4.3 Reporting of SAEs and AEs to FDA

As Collectar Biosciences holds the IND for CLR 131, they assume responsibility for reporting all events in accordance with FDA 21 CFR 312.32. Collectar has contracted with a CRO, Medpace for SAE management for the IND.

Medpace clinical Safety Contact information:

US: [contact], dial 3
Or [name], dial 3
[contact]
Or [name]

Email: [contact]

11.4.4 Reporting of Pregnancy

- Pregnancy will be reported from time of first study drug until 85 days after discontinuation of CLR 131.
- Pregnancy will be reported to UW within 1 business day of discovery of the event.

To ensure subject safety, each pregnancy in a subject on study treatment will be reported to UW within 1 business day of learning of its occurrence. The pregnancy will be followed to determine outcome, including spontaneous or voluntary termination, details of the birth, and the presence or absence of any birth defects, congenital abnormalities, or maternal and/or newborn complications.

11.5 Halting Rules

During the conduct of this study, adverse events and serious adverse events that are categorized as probably related to CLR 131 will be evaluated and analyzed weekly by the principal investigators. If >25 % of subjects have serious adverse events that are probably related to CLR 131 treatment, then enrollment for the study will be suspended for further analysis.

Subsequent review of serious, unexpected, and related AEs will be evaluated by the DSMC, IRB, Collectar Biosciences. Collectar Biosciences and local regulatory authorities retain the authority to suspend additional enrollment and administration of CLR 131 for the entire study, as applicable.

12 STUDY OVERSIGHT

The UWCCC Data and Safety Monitoring Committee (DSMC) is responsible for the regular review and monitoring of ongoing clinical research in the UWCCC. A summary of DSMC activities are as follows:

- Review clinical trials conducted at the UWCCC for subject safety, protocol compliance, and data integrity.
- Review Serious Adverse Events (SAE) requiring expedited reporting, as defined in the protocol, for clinical trials conducted at the UWCCC, and studies conducted at external sites for which the UWCCC acts as an oversight body.
- Review reports generated through the UWCCC DSMS elements (Internal Audits, Quality Assurance Reviews, Response Reviews, Compliance Reviews, and Protocol Summary Reports).
- Notify the protocol Principal Investigator of DSMC decisions and, if applicable, any requirements for corrective action related to data or safety issues.
- Work in conjunction with the UW Health Sciences IRB in the review of relevant safety information as well as protocol deviations, non-compliance, and unanticipated problems reported by the UWCCC research staff, when appropriate.
- Ensure notification of SAEs which require expedited reporting are provided to external sites participating in multi-institutional clinical trials coordinated by the UWCCC.

Monitoring and Reporting Guidelines

UWCCC quality assurance and monitoring activities are determined by study sponsorship and risk level of the protocol as determined by the PRMC. All protocols (including Intervention Trials, Non-Intervention Trials, Behavioral and Nutritional Studies, and trials conducted under a Training Grant) are evaluated by the PRMC at the time of committee review. UWCCC monitoring requirements for trials without an acceptable external DSMB are as follows:

Intensive Monitoring

Protocols subject to intensive monitoring generally include UW Institutional Phase I. These protocols undergo review of subject safety at regularly scheduled DOT meetings where the results of each subject's treatment are discussed, and the discussion is documented in the DOT meeting minutes. The discussion includes the number of subjects enrolled, significant toxicities, dose adjustments, and responses observed. Protocol Summary Reports are submitted on a quarterly basis by the study team for review by UWCCC DSMC. All reports from the UWCCC DSMC will be provided to Collectar Biosciences.

Review and Oversight Requirements

- Study Progress Review
 - Protocol Summary Reports (PSR) are required to be submitted to UWCCC DSMC quarterly. The PSR provides a cumulative report of SAEs, as well as instances of noncompliance, protocol deviations, and unanticipated problems, toxicities and responses that have occurred on the protocol in the timeframe specified. PSRs for those protocols scheduled for review are reviewed at each DSMC meeting.
 - Protocol Summary Reports enable DSMC committee members to assess whether significant benefits or risks are occurring that would warrant study suspension or closure. This information is evaluated by the DSMC in conjunction with other reports of quality assurance activities (e.g., reports from Internal Audits, Quality Assurance Reviews, etc.) occurring since the prior review of the protocol by the DSMC.
 - In the event that there is significant risk warranting study suspension or closure, the UWCCC DSMC will notify the PI of the findings and ensure the appropriate action is taken for the protocol (e.g., suspension or closure). The DSMC ensures that the PI reports any temporary or permanent suspension of a clinical trial to the appropriate agencies. Any UWCCC DSMC findings and requirements for follow-up action are submitted to the UWCCC CRC.

13 CLINICAL SITE MONITORING

Collectar Biosciences or their designee may periodically monitor the data for the study. A clinical monitor will make regularly scheduled trips to the clinical sites to review the progress of the study. The actual frequency of monitoring trips will depend on the enrollment rate and performance at the site. At each visit, the monitor will review various aspects of the study including, but not limited to, screening and enrollment logs, compliance with the protocol and with the principles of ICH GCP, completion of CRFs, source data verification, and study drug accountability and storage.

In addition to the above, a representative from Collectar Biosciences' auditing staff or government inspectors may review the conduct/results of the study at the clinical site. The Investigator must promptly notify Collectar Biosciences of any audit requests by regulatory authorities.

14 STATISTICAL CONSIDERATIONS

14.1 Study Hypotheses

Reducing the dose of external beam radiation therapy, when given in combination with CLR 131, will be safe and tolerable while maintaining favorable tumor response rates and diminishing the adverse impact of radiation treatment on subject specific symptoms, such as quality of life, salivary flow and swallowing function.

14.2 Sample Size Considerations

An mTPI-2 design, an extension of modified toxicity probability interval (mTPI-2), will be used to identify the MTD using cohorts of 4 subjects and up to 3 dose levels of CLR 131 (Ji *et al.*, 2007; Ji & Wang, 2013). The first 4 subjects will be treated at Dose Level 1. The maximum number of subjects treated at a dose level will be 8, with one exception: if 1 out of 8 subjects experiences a DLT at Dose Level 1, the study team will consider the possibility of treating 2 additional subjects at Dose Level 1. The trial can be monitored using columns 4 and 8 of [Table 3](#) below, which contains the dose-escalation rules. Dose escalation will not be confirmed until all subjects in cohort recover to non-DLT levels or meet the criteria above. If 0 out of 4 subjects experiences a DLT at Dose Level 2, the study will move directly to the expansion phase.

Dose Level	Doses* of CLR 131
-1	12.5 mCi/m ²
1**	15.6 mCi/m ²
2	18.75 mCi/m ²

*Dose level listed is administered on first on day 1 and again on day 8.

**The first 4 subjects will be treated at dose level 1. Dose level -1 will be used as a de-escalation dose.

Table 3: Dose escalation rules

	1	2	3	4	5	6	7	8	9	10
0	E	E	E	E	E	E	E	E	E	E
1	D	D	D	S	S	S	S	S	S	E
2		DU	DU	D	D	D	S	S	S	S
3			DU	DU	DU	DU	D	D	D	D
4				DU	DU	DU	DU	DU	DU	D
5					DU	DU	DU	DU	DU	DU
6						DU	DU	DU	DU	DU
7							DU	DU	DU	DU
8								DU	DU	DU
9									DU	DU
10										DU

Column indicates the number of subjects treated. Row indicates the number of subjects with DLTs. **E**: Escalate to the next higher dose; **S**: Stay at the same dose; **D**: De-escalate to the previous lower dose; **DU**: De-escalate to the previous lower dose and the current dose will never be used again in the trial; sample size = **10**, target toxicity probability = **0.2**, epsilon 1 =**0.1**, epsilon 2 =**0.1**.

The number of participants treated in the expansion cohort is dependent on the number of participants treated at the MTD in the dose escalation phase using the the mTPI-2 design. Up to 12 subjects will be treated at the MTD. Statistical analysis for outcomes is based on participants treated at the MTD, including dose escalation patients treated at the MTD.

In recent years, the head and neck oncology program at UW has evaluated approximately 75-100 patients per year with recurrent HNC. We estimate that approximately half of these patients would be potential candidates for this trial. Assuming enrollment of 50 % of eligible patients, and CLR 131 uptake in 75 % of subjects administered a dosimetry test dose, we anticipate no problems to accrue the necessary subjects over 24 months.

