Once the MTD is determined by the dose escalation phase, participants will be enrolled on the dose expansion cohort. Participants on the dose expansion cohort will receive 2 doses of CLR 131 with the first dose on day 1 followed by

the second dose on day 8, with the dose determined by the dose escalation phase.

SPECT/CT imaging will be performed on days 2, 3, 4-6, and 7-8 of the treatment period to visualize and quantitate the biodistribution of CLR 131. Based on these SPECT/CT imaging scans, the [name] lab will utilize the Monte Carlo method to predict absorbed dose of CLR 131 to tumors and normal structures.

All subjects will start thyroid-protection medication the day prior to the CLR 131 dosimetry test dose and will continue to take thyroid protection medication for 14 days after the last CLR 131 dose.

Based on the calculated absorbed dose of CLR 131 to the specific targeted tissue, the subject will undergo external beam radiation therapy (EBRT) to complete the designated radiation dose outlined in the re-irradiation plan, as per standard of care. Prior to CLR 131 administration and at 3 and 6 months post EBRT, subjects will be assessed for changes to swallow function. Prior to CLR 131 administration and at 3, 6 and 12 months post EBRT, quality of life measures and salivary characteristics will be assessed. We anticipate the total study (baseline, CLR 131 administration, EBRT and 3, 6, 12 and 24 month follow up assessments) to take 27 months per participant.

Study Duration: 47 months

[figure not shown]
Subject Participation Duration: 27 months

Estimated Time to Complete Enrollment: 20 months

Date Accrual Goal Met / Study Closed to Accrual April 18, 2022

Date DLT window completed by last participant June 16, 2022

Schematic of Study Design:

***Approximately 6 safety labs will coincide with SOC EBRT visits, and 6 safety lab visits will fall outside of the SOC EBRT visits.**

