CLR 131 in combination with dexamethasone is currently under investigation in a Phase 1 trial in subjects with relapsed/refractory multiple myeloma (MM) following treatment with both a proteasome inhibitor and an immunomodulatory agent. All subjects have been heavily pretreated. Seven dose cohorts were examined: 12.5 mCi/m², 18.75 mCi/m², 25 mCi/m², 31.25 mCi/m², and a multiple dose cohorts of 15.625 mCi/m², 18.75 mCi/m² and 20 mCi/m² administered twice, all in combination with 40 mg dexamethasone weekly. Thirty-one patients were dosed and the independent Data Monitoring Committee confirmed seven dose levels safe and tolerated. The overall response rate for patients receiving <60 mCi total body dose was 7% (1/15) and 27% (3/11) for patients receiving a ≥60 mCi total body dose. All evaluable patients achieved a minimum of stable disease, with at least one patient at each dose level achieving at least a minor response. CLR 131 has been shown to be well tolerated with the majority of adverse events being considered mild to moderate. The most common treatment emergent adverse events were cytopenias, primarily thrombocytopenia, with very predictable onset, time to nadir and recovery. Beyond cytopenias, fatigue was also a frequently reported adverse event. .

CLR 131 is also under investigation in a Phase 2 study in relapsed or refractory B-Cell malignancies (CLOVER-1) where 56 patients have been enrolled to date. Patients received either < 60 or ≥ 60 mCi total body dose CLR 131 (25 mCi/m² single bolus, 31.25 mCi/m² fractionated or 37.5mCi/m² fractionated) either as a bolus dose or fractionated with half on day 1 and half on day 7 ± 1 day. Patients enrolled in the final dosing group in Part A (Group 4) received an alternate two cycle fractionated dose schedule: fractionated 30 mCi/m² CLR 131 as 15 mCi/m² on Day 1, Day 15 (±1 day) for the first cycle, and then repeated Day 57 (± 1 day), and Day 71 (± 1 day) for the second cycle (total body dose ≥ 60 mCi). The adverse event profile remains consistent with the Phase 1 trial, with the primary treatment emergent adverse events including cytopenias; most

commonly thrombocytopenia. The time to onset, nadir, and recovery continue to be predictable and the events manageable. Fatigue has also been reported commonly.

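### Zero DLTs in four subjects at the top dose opens expansion at a dose treated as the MTD, although the 20% DLT target has not been bracketed

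*Combined protocol and SAP*

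**What the plan says.** Section 14.2 states that the mTPI-2 design "will be used to identify the MTD using cohorts of 4 subjects and up to 3 dose levels of CLR 131". The footnote to Table 3 gives "target toxicity probability = 0.2, epsilon 1 =0.1, epsilon 2 =0.1", which is a target interval of 0.10 to 0.30. Of the three levels, -1 is for de-escalation only, so Dose Level 2 is the single step above the start and the highest level. On size, "The maximum number of subjects treated at a dose level will be 8, with one exception": two more subjects may be considered at Dose Level 1 after 1/8 DLTs.

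The rule at the top is "If 0 out of 4 subjects experiences a DLT at Dose Level 2, the study will move directly to the expansion phase". In Table 3 that same result, 0 of 4, is E.

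The Protocol Summary (Description of Intervention) says "Once the MTD is determined by the dose escalation phase, participants will be enrolled on the dose expansion cohort". Sections 5.1 and 14.2 plan up to 12 subjects at the MTD, and 14.2 bases the outcome analysis on subjects treated there, including those from escalation. No section defines the MTD, gives a rule for selecting it, or provides a conclusion for a range in which it is not found.

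**The concern.** E tells the team to go higher. When there is nowhere higher to go, the usual conclusion is that the highest planned dose was reached without finding the limit. This plan instead moves to expansion, and its other sentences allow expansion only at the MTD. The label then follows from having run out of levels and not from any observed relation to the 20% target. With a true DLT rate of zero, the rule returns Dose Level 2 every time.

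The lower end has a matching gap. D and DU mean moving to the previous lower dose, and Dose Level -1 has none.

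At stake is the trial's dose conclusion. If a dose is reported as an MTD from a design with a stated 20% target, a reader can fairly take it as a dose located against that target. After 0/4 it has not been.

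**Working it through.** **Inputs.** From 14.2: cohorts of 4, start at Dose Level 1, target interval 0.10 to 0.30, at most 8 per level, optional 2 more at Dose Level 1 after 1/8, and 0/4 at Dose Level 2 to expansion. Assumed, because the documents do not state them: a Beta(1,1) prior; DU when P(p > 0.2) exceeds 0.95; return to a level allowed after D but not after DU. The true DLT rates are also assumed, over a range.

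**Step 1: reproduce Table 3.** mTPI-2 compares posterior probability per unit width across intervals. For 0/4 the posterior is Beta(1,5):
- P(p < 0.1) = 1 − 0.9^5 = 0.410; divided by width 0.1 = 4.10
- P(0.1 < p < 0.3) = 0.9^5 − 0.7^5 = 0.422; divided by width 0.2 = 2.11
- P(p > 0.3) = 0.7^5 = 0.168

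The first interval has the greatest density, so the decision is E, as printed. Over the whole table 64 of 65 cells match, including all of columns 4, 8 and 10. The exception, 1 DLT in 1 subject (computed DU, printed D), is never used with cohorts of four.

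**Step 2: probability of expansion at Dose Level 2 on 0/4.** Let p1 and p2 be the true DLT rates at Levels 1 and 2. Without the extension the only route is 0/4 at Level 1, then 0/4 at Level 2:

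(1 − p1)^4 × (1 − p2)^4

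If the extension is always used, one more route opens: 1/4, then 0/4, then 0/2 at Level 1 (1/10, which reads E), then 0/4 at Level 2:

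(1 − p2)^4 × [(1 − p1)^4 + 4·p1·(1 − p1)^9]

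For a flat 10%: 0.9^8 = 0.430, and 0.430 + 0.4 × 0.9^13 = 0.532.

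| True rates (Levels -1/1/2) | Without extension | With extension |
|---|---|---|
| flat 2% | 85% | 91% |
| flat 5% | 66% | 77% |
| flat 10% | 43% | 53% |
| flat 20% | 17% | 21% |
| 10/20/30% | 10% | 12% |

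With a flat rate, the probability exceeds one half only below 1 − 0.5^(1/8) = 8.3% without the extension, or about 10.8% with it.

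**Step 3: separate this from every selection of Dose Level 2.** With 5% at Level 1 and 10% at Level 2, Level 2 is selected in 78.1% (90.2% with the extension) of trials, but on 0/4 in 53.4% (61.7%). The remaining 24.7 (28.5) percentage points end in S at 1/8 or 2/8. Those are observed rates of 12.5% or 25%, inside the target interval, and they are legitimate MTD results. A result of 0/8 cannot occur at Level 2 during escalation, because 0/4 leaves escalation at once.

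**Step 4: what zero DLTs can say.** One-sided 95% exact upper limits are 1 − 0.05^(1/4) = 52.7% for 0/4 and 1 − 0.05^(1/12) = 22.1% for 0/12. Neither excludes 20%.

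**Step 5: the lower end.** D or DU at Dose Level -1 occurs in about 7% of trials at a flat 20%, 13% at 20/30/40% and 52 to 53% at a flat 40%.

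**Step 6: after expansion.** Table 3 stops at 10 subjects, while up to 12 may be treated. Under the same assumptions 4/12 (posterior Beta(5,9)) gives P(0.1 to 0.3) = 0.9935 − 0.6543 = 0.339 and P(0.3 to 0.5) = 0.6543 − 0.1334 = 0.521. The widths are equal, so the decision is D. A dose selected on 0/4 can therefore read as too toxic later, and the plan gives no label for that.

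**The case against.** The strongest reply has five parts.

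- **The protocol never says in terms that Dose Level 2 is named the MTD.** True: it is an inference from the Protocol Summary and 14.2. But those sentences leave no other basis on which expansion could open.
- **The result may be uncommon.** This stands. At or near the target rate it is a minority outcome.
- **0/4 does not put the dose far from 20%.** This also stands. The posterior in Step 1 gives almost equal probability to rates below 0.1 and rates within 0.1 to 0.3. It supports leaving the dose unlabelled, since the rate has not been located in either direction.
- **Stopping for toxicity is already possible.** Section 5.7 allows termination for unacceptable toxicity, and 11.5 suspends enrolment if more than 25% have probably related serious adverse events. Those provisions can halt the trial, but they supply no dose conclusion at either end of the range.
- **The uncertainty will be visible.** The primary outcome is adverse-event incidence, with exact intervals under 14.3.1, and up to 12 subjects will contribute. That softens the consequence without correcting the label.

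The Protocol Summary also records that accrual closed in April 2022 and the last DLT window ended in June 2022. What remains is how the dose is reported, which is where the remedy applies.

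**Conclusion.** The point holds as a gap in the conclusion rule. After 0/4 at Dose Level 2 the plan treats that level as the MTD with no DLT seen there and the 20% target not bracketed, and it has no conclusion for D or DU at Dose Level -1. The probability of the first outcome runs from 85-91% at a flat 2% to 10-12% at 10/20/30%. It rests on the assumed true rates, prior and re-entry rule given above.

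A reader might infer that the MTD will usually be declared this way, because 2.1.3.3 reports of the myeloma trial that "Thirty-one patients were dosed and the independent Data Monitoring Committee confirmed seven dose levels safe and tolerated", and those levels included 15.625, 18.75 and 20 mCi/m² given twice. The documents do not support that step. They give no DLT rate, the disease differs, and 2.3.1.1 says this is the first study combining CLR 131 with EBRT. Every subject here also receives a 15 mCi test dose. At Dose Level 2 the total is 2 × 18.75 + 15/BSA, which is 43.5 mCi/m² at the 2.5 m² cap and 45.8 at an assumed 1.8 m². The highest two-dose myeloma cohort totals 40, with no test dose mentioned. Low DLT rates are possible but not established.

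**What to change.** Add a reporting rule to 14.2, with matching wording in 5.1 and the Protocol Summary:

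- Report an MTD only if a higher tested level was rejected (D or DU), or if the escalation-phase decision at the selected level was S.
- If Dose Level 2 is selected on 0/4 (E), report *highest dose administered; MTD not reached*, with the observed DLT rate and its exact upper limit over all subjects treated at that dose, including expansion.
- If the mTPI-2 rule, recomputed for the number actually treated (up to 12, beyond Table 3), gives D or DU at the selected dose after expansion, report that the dose exceeded the target and do not call it the MTD.
- If Dose Level -1 returns D or DU, report *no MTD identified in the range tested*. Table 3 and the absence of a lower level must be reconciled.
- In the analysis-set sentences, refer to subjects treated at the selected dose.

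The cost is wording. No dose, enrolment or treatment rule changes, and no data are added. The downside is that the trial may have to report that it did not identify an MTD.

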Resulting in hospitalization \geq 24 hrs	10 Calendar Days	24 Hour; 5 Calendar Days
Not resulting in Hospitalization \geq 24 hrs	Not required	

***Planned hospitalizations for disease-related surgery, routine procedures (such as G-tube placement), non-disease-related procedures, and inpatient hospitalization for radiation protection/exposure levels are not considered SAEs. A hematologic adverse event grade 1-4 will not be defined as an SAE if it can be managed with blood product transfusions, unless it exceeds the window for a dose limiting toxicity.**

Expedited AE reporting timelines are defined as:

- **24-Hour; 5 Calendar Days** – The AE must initially be reported within 24 hours of learning of the AE, followed by a complete expedited report within 5 calendar days of the initial 24-hour report.
- **10 Calendar Days** – A complete expedited report on the AE must be submitted within 10 calendar days of learning of the AE.

Serious adverse events that occur more than 28 days after last EBRT treatment or 85 days after first treatment dose of CLR 131, whichever is later and have an attribution of possible, probable, or definite require reporting as follows:

Expedited 24-hour notification followed by complete report within 5 calendar days for:

- All Grade 3, 4, and 5 AEs

Expedited 10 calendar day reports for:

- Grade 2 AEs resulting in hospitalization or prolongation of hospitalization

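### After 0/4 DLTs at Dose Level 2, Section 14.2 gives no DLT boundary and no re-evaluation of the MTD for the up to 8 expansion subjects treated at that dose

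*Combined protocol and SAP*

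**What the plan says.** Section 14.2 uses an mTPI-2 design "using cohorts of 4 subjects and up to 3 dose levels of CLR 131", with "target toxicity probability = 0.2, epsilon 1 =0.1, epsilon 2 =0.1". On numbers per level it says: "The maximum number of subjects treated at a dose level will be 8, with one exception". The exception concerns Dose Level 1 only. On looks it says "The trial can be monitored using columns 4 and 8 of" Table 3, whose title refers to dose escalation and whose last column is 10 subjects.

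Dose Level 2 is the top level. For it the section adds: "If 0 out of 4 subjects experiences a DLT at Dose Level 2, the study will move directly to the expansion phase". It then allows expansion: "Up to 12 subjects will be treated at the MTD". The Protocol Summary (Description of Intervention) opens expansion once escalation has determined the MTD.

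Section 14.3.1 plans frequency tables of adverse events with exact intervals. It does not mention DLTs or confirmation of the MTD.

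Outside Section 14, the halting rule in 11.5 suspends enrollment for further analysis under this condition: "If >25 % of subjects have serious adverse events that are probably related to CLR 131 treatment". Section 12 gives the DSMC quarterly reports and a route to suspension or closure. Section 5.7 lists unacceptable toxicity among the reasons to stop.

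**The concern.** A clean first cohort at the top dose skips the column 8 look that the escalation scheme otherwise provides. The MTD is then settled on 4 subjects, although DLT data may come from as many as 12 at that dose. The plan does not say what those later DLTs mean for the MTD.

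This makes the conclusion depend on the order of events. With 1 DLT in the first 4 at Dose Level 2, Table 3 reads S, 4 more are treated, and 3/8 reads D. With 0 in the first 4 and 3 in the next 4, the dose, the count and the denominator are the same, but the trial is already in expansion and no action is clearly written. At 12 subjects Table 3 has no column at all. What is at stake is the main dose conclusion of a Phase 1 trial, and how DLTs among expansion subjects bear on it.

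**Working it through.** **Inputs.** From Section 14.2: target 0.20; epsilons 0.1 and 0.1, so an equivalence interval of 0.10 to 0.30; cohorts of 4; direct move after 0/4 at Dose Level 2; up to 12 at the MTD. Assumed, because the documents do not state them: a uniform Beta(1,1) prior, a DU cutoff of P(p > 0.2) > 0.95, and the true DLT rates.

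**Step 1: reproduce Table 3.** With x DLTs in n subjects the posterior is Beta(1 + x, 1 + n − x). Divide 0 to 1 into subintervals of width 0.2 on either side of 0.10–0.30, shorter at the ends. The subinterval with the largest posterior mass per unit width gives the decision, and DU overrides it if P(p > 0.2) > 0.95. This matches 64 of 65 cells. The exception is 1 DLT in 1 subject (table D, computed DU), which is never used with cohorts of 4. Columns 4 and 8 match exactly.

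**Step 2: extend to n = 12.** The same calculation gives the following.

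| DLTs in 12 | Mass per unit width, 0.1–0.3 | Largest elsewhere | P(p > 0.2) | Reading |
|---|---|---|---|---|
| 1 | 2.79 | 3.79 (0–0.1) | 0.234 | E |
| 2 | 3.32 | 1.34 (0–0.1) | 0.502 | S |
| 3 | 2.73 | 1.87 (0.3–0.5) | 0.747 | S |
| 4 | 1.70 | 2.60 (0.3–0.5) | 0.901 | D |
| 5 | 0.82 | 2.72 (0.3–0.5) | 0.970 | DU |

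So at n = 12, 0–1 is E, 2–3 S, 4 D, and 5 or more DU. Column 11 reads the same.

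**Step 3: how much 0/4 shows.** The exact two-sided 95% upper limit is 1 − 0.025^(1/4) = 0.602. The chance of 0/4 at true rate p is (1 − p)^4; at p = 0.30 this is 0.7^4 = 0.240.

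**Step 4: what the plan's own rule would read, given 0/4.** Let A be the DLTs in the next 4 subjects and B those in the 4 after that, each Binomial(4, p). With looks at n = 8 and 12, a D or DU reading needs A ≥ 3, or A ≤ 2 with A + B ≥ 4. At p = 0.30 this is 0.084 + 0.129 = 0.212. A look at n = 10 adds the Table 3 boundary of 3 or more.

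| True DLT rate (assumed) | P(0/4) | D or DU given 0/4, looks at 8 and 12 | Looks at 8, 10 and 12 | P(0/4) × looks at 8 and 12 |
|---|---|---|---|---|
| 20% | 41% | 7% | 11% | 2.7% |
| 30% | 24% | 21% | 28% | 5.1% |
| 35% | 18% | 31% | 39% | 5.6% |
| 40% | 13% | 43% | 51% | 5.5% |

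**Step 5: what 11.5 would do instead.** Assume generously that every DLT is a probably related SAE, that there were no earlier SAEs, and that the rule is checked after each expansion subject. If the denominator is Dose Level 2 subjects only, more than 25% of 12 means 4 by the end. The rule then triggers in 19, 40 and 62% of cases at true rates of 20, 30 and 40%. If it is all subjects, with 4 assumed at Dose Level 1, more than 25% of 16 means 5, and the figures are 4, 13 and 30%. Section 11.5 does not say which denominator applies.

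**The case against.** A reader might infer that an over-toxic dose would be kept whatever expansion shows. The documents do not support that. Section 11.5 is study-wide, with weekly review, and Step 5 shows that it can trigger in expansion. The DSMC and Section 5.7 also apply throughout.

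A reader might also infer that the halting rule misses the main expected toxicity, because Table 2's footnote says "A hematologic adverse event grade 1-4 will not be defined as an SAE if it can be managed with blood product transfusions". The same sentence withdraws that exemption once the event outlasts the DLT window. Shorter cytopenias that are managed by transfusion are not DLTs under 2.3.1.1.2 either, so a DLT rule would not count them.

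The sentence on columns 4 and 8 speaks of the trial, not of escalation, and DU bars a dose for the rest of the trial. After 0/4 at Dose Level 2, n = 8 can be reached at that dose only in expansion. That reading is possible, but the text gives no consequence for an MTD already declared, and n = 12 stays uncovered.

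The dose does not rest on 4 subjects alone. Reaching Dose Level 2 requires an E reading at Dose Level 1, and 2.1.3.3 lists 18.75 mCi/m² given twice among the myeloma levels judged safe. Those patients received it with dexamethasone, whereas 2.3.1.1 calls this trial the first to combine CLR 131 with EBRT.

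What stands from these objections is that oversight exists and the unconditional probabilities are small. What they do not supply is a DLT rule. Section 11.5 needs SAEs that are probably related, while a non-hematologic DLT needs only a possible relation and need not be serious. The consequence under 11.5 is suspension for analysis, not a decision on the MTD.

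**Conclusion.** The concern holds in this limited form: on the 0/4 path there is no prespecified DLT boundary and no MTD re-evaluation in expansion, only a general SAE halt and DSMC oversight. Identical DLT data at Dose Level 2 can therefore be handled differently according to their order. A result of 4/12, which is D under the plan's own algorithm, has no written effect on the MTD.

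Given 0/4, the plan's rule at n = 8 and 12 would question the dose in 21 to 43% of cases at true rates of 30 to 40%. The joint chance of 0/4 followed by such a reading is 5 to 6%. These figures rest on the assumed true rates, the uniform prior and the 0.95 cutoff; the reproduction of columns 4 and 8 supports the last two. It would be wrong to describe the chance of stopping expansion as zero: what is missing is a formal mTPI-2 reading and its meaning for the MTD. This should be corrected, because it bears on the main dose conclusion and is cheap to repair.

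**What to change.** In Section 14.2, reconcile the direct-to-expansion sentence with Table 3:

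- State that the mTPI-2 assessment continues on all subjects treated at the selected dose, and name the looks (n = 8 and 12, or 8, 10 and 12).
- Add columns 11 and 12 to Table 3 by the same calculation: 0–1 E, 2–3 S, 4 D, 5 or more DU. State the prior and the DU cutoff.
- Confirm and report the MTD only from pooled escalation and expansion DLTs, with an exact interval. Section 14.2 already pools these subjects for outcomes.
- Say how a D or DU reading relates to the halting rule in 11.5, and define that rule's denominator. The clinical action remains with the sponsor and the DSMC.

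The Protocol Summary records accrual closed on April 18, 2022 and the last DLT window completed on June 16, 2022. If added now, the text can govern only how the MTD is assessed and reported, and should be labelled post hoc.

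The cost is about one paragraph and two table columns. The statistical price, given 0/4, is a 7 to 11% chance of a D or DU reading when the true rate equals the 20% target.
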